## 9.2. APPENDIX II - PROGRAMMING CONVENTIONS

#### **DATES & TIMES**

Document: \\SW20RND01\\VistaTempDir\Temp28232\\Shire\_0624\_209\_SAP\_v1 0.docx

Author: Version Number: 1.0
Version Date: 21Jul2017

Template No: CS TP BS016 Revision 4 Reference: CS WI BS005

Effective Date: 01Apr2016

Copyright © 2009, 2010, 2012, 2016 Quintiles Transnational Corp. All rights reserved.

The contents of this document are confidential and proprietary to Quintiles Transnational Corp. Unauthorized use, disclosure or reproduction is strictly prohibited.

PROTOCOL: 0624 Page 32 of 35

Depending on data available, dates and times will take the form yyyy-mm-ddThh:mm:ss.

#### **SPELLING FORMAT**

English US.

#### **PRESENTATION OF TREATMENT GROUPS**

For outputs, treatment groups will be represented as follows and in that order:

Treatment Group	For Tables, Listings and Graphs
Cinryze 500 U	Cinryze 500 U
Cinryze 1000 U	Cinryze 1000 U

#### **PRESENTATION OF VISITS**

For outputs, visits will be represented as follows and in that order:

Long Name (default)	Short Name
Screening	Scr
Dosing Visit 1	V1
Dosing Visit 2	V2
Dosing Visit 24	V24

#### LISTINGS

All listings will be ordered by the following: Cinryze 500 U then Cinryze 1000 U.

#### 9.3. APPENDIX III - PARTIAL DATE CONVENTIONS

Imputed dates will NOT be presented in the listings.

\\SW20RND01\VistaTempDir\Temp28232\Shire\_0624\_209\_SAP\_v1 0.docx Document:

Version Number: Author: 1.0 Version Date: 21Jul2017

Template No: CS\_TP\_BS016 Revision 4 Effective Date: 01Apr2016 Reference: CS\_WI\_BS005

Copyright © 2009, 2010, 2012, 2016 Quintiles Transnational Corp. All rights reserved.

The contents of this document are confidential and proprietary to Quintiles Transnational Corp. Unauthorized use, disclosure or reproduction is strictly prohibited.

PROTOCOL: 0624-209 Page 33 of 35

## **ALGORITHM FOR TREATMENT EMERGENCE OF ADVERSE EVENTS**

START DATE	STOP DATE	ACTION	
Known	Known	If start date < study med start date, then not TEAE	
		If start date >= study med start date, then TEAE	
	Partial	If start date < study med start date, then not TEAE	
		If start date >= study med start date, then TEAE	
	Missing	If start date < study med start date, then not TEAE	
		If start date >= study med start date, then TEAE	
Partial, but known components show that it cannot be on or after study med start date	Known	Not TEAE	
	Partial	Not TEAE	
	Missing	Not TEAE	
Partial, could be on or	Known	If stop date < study med start date, then not TEAE	
after study med start date		If stop date >= study med start date, then TEAE	
	Partial	Impute stop date as latest possible date (i.e. last day of month if day unknown or 31st December if day and month are unknown), then:	
		If stop date < study med start date, then not TEAE	
		If stop date >= study med start date, then TEAE	
	Missing	Assumed TEAE	

\\SW20RND01\\VistaTempDir\Temp28232\\Shire\_0624\_209\_SAP\_v1 0.docx PPD \qquad \text{Version Number:} Document:

Author: 1.0 Version Date: 21Jul2017

Template No: CS\_TP\_BS016 Revision 4 Effective Date: 01Apr2016 Reference: CS\_WI\_BS005

Shire
PROTOCOL: 0624-209
Page 34 of 35

START DATE	STOP DATE	ACTION
Missing	Known	If stop date < study med start date, then not TEAE  If stop date >= study med start date, then TEAE
	Partial	Impute stop date as latest possible date (i.e. last day of month if day unknown or 31st December if day and month are unknown), then:
		If stop date < study med start date, then not TEAE
		If stop date >= study med start date, then TEAE
	Missing	Assumed TEAE

# **ALGORITHM FOR PRIOR / CONCOMITANT MEDICATIONS**

START DATE	STOP DATE	ACTION
Known	Known	If stop date < study med start date, assign as prior If stop date >= study med start date and start date <= end of treatment, assign as concomitant If stop date >= study med start date and start date > end of treatment, assign as post study
	Partial	Impute stop date as latest possible date (i.e. last day of month if day unknown or 31 st December if day and month are unknown), then:  If stop date < study med start date, assign as prior  If stop date >= study med start date and start date <= end of treatment, assign as concomitant  If stop date >= study med start date and start date > end of treatment, assign as post treatment
	Missing	If stop date is missing could never be assumed a prior medication If start date <= end of treatment, assign as concomitant If start date > end of treatment, assign as post treatment

\\SW20RND01\\VistaTempDir\Temp28232\\Shire\_0624\_209\_SAP\_v1 0.docx PPD \qquad \text{Version Number:} Document:

Author: 1.0 Version Date: 21Jul2017

Template No: CS\_TP\_BS016 Revision 4 Effective Date: 01Apr2016 Reference: CS\_WI\_BS005

Copyright © 2009, 2010, 2012, 2016 Quintiles Transnational Corp. All rights reserved. The contents of this document are confidential and proprietary to Quintiles Transnational Corp. Unauthorized use, disclosure or reproduction is strictly prohibited.

STOP DATE	ACTION
Known	Impute start date as earliest possible date (i.e. first day of month if day unknown or 1st January if day and month are unknown), then:  If stop date < study med start date, assign as prior  If stop date >= study med start date and start date <= end of treatment, assign as concomitant  If stop date >= study med start date and start date > end of treatment, assign as post treatment
Partial	Impute start date as earliest possible date (i.e. first day of month if day unknown or 1 st January if day and month are unknown) and impute stop date as latest possible date (i.e. last day of month if day unknown or 31 st December if day and month are unknown), then:  If stop date < study med start date, assign as prior  If stop date >= study med start date and start date <= end of treatment, assign as concomitant  If stop date >= study med start date and start date > end of treatment, assign as post treatment
Missing	Impute start date as earliest possible date (i.e. first day of month if day unknown or 1 st January if day and month are unknown), then:  If stop date is missing could never be assumed a prior medication  If start date <= end of treatment, assign as concomitant  If start date > end of treatment, assign as post treatment
Known	If stop date < study med start date, assign as prior If stop date >= study med start date, assign as concomitant Cannot be assigned as 'post treatment'
Partial	Impute stop date as latest possible date (i.e. last day of month if day unknown or 31 st December if day and month are unknown), then:  If stop date < study med start date, assign as prior  If stop date >= study med start date, assign as concomitant  Cannot be assigned as 'post treatment'  Assign as concomitant
	DATE Known  Partial  Missing  Known

\\SW20RND01\\VistaTempDir\Temp28232\\Shire\_0624\_209\_SAP\_v1 0.docx PPD \\Version \Number: Document:

Author: 1.0 21Jul2017 Version Date:

Template No: CS\_TP\_BS016 Revision 4 Effective Date: 01Apr2016 Reference: CS\_WI\_BS005

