6.5.2 Concomitant Medications

Concomitant medications taken from the start of dosing (Dosing Visit 1) through the 1-Month Post-treatment Follow-up Visit will be recorded in the CRF. For medications associated with the management of angioedema attacks, study personnel will record the start and stop dates, dose, unit, frequency, route of administration, and indication in the subject's CRF. For medications not associated with the management of HAE, study personnel will record the start and stop dates (if known), route of administration, and indication for which the medication was administered in the subject's CRF.

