#### 5.8.7. PRIOR AND CONCOMITANT MEDICATION

Prior medications are any medications received for the management of HAE within 12 months before Day 1 and all other medications taken within 1 week before Dosing Visit 1.

Concomitant medications are any medications taken from the start of Dosing Visit 1 through the 1-Month Post-treatment Follow-up Visit.

Prior and concomitant medications will be coded according to World Health Organization (WHO) drug dictionary version 01JUN2016. Summary of medications will be divided into medications given for HAE long-term prevention, HAE short-term prevention, HAE acute treatment which included either C1 Inhibitor or Tranexamic Acid, HAE symptom management which indication included acute treatment and medication is not C1 Inhibitor or Tranexamic Acid, and all other medications used. This will be presented by ATC Level 1 and PT. Preferred Term is defined as basename from WHO drug dictionary. Table will be sorted by indications and ATC Level 1 in alphabetical order, then within ATC Level 1, PT will be sorted in descending frequency. Details of prior and concomitant medications used will be provided in one listing.

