## 9. APPENDICES

# 9.1. APPENDIX I – LIST OF STATISTICAL OUTPUTS

#### 9.1.1. LIST OF PLANNED TABLES

Table 14.1.1.1 Subject Disposition (All Screened Subjects)

Table 14.1.2.1 Protocol Deviations (Intent-to-Treat Safety Analysis Set)

Table 14.1.4.1 Demographic and Baseline Characteristics (Intent-to-Treat Safety Analysis Set)

Table 14.1.4.3.1 Summary of HAE History (Intent-to-Treat Safety Analysis Set)

Table 14.1.4.3.2 Summary of Medical History (Intent-to-Treat Safety Analysis Set)

Table 14.1.4.4 Prior Medications and Therapy (Intent-to-Treat Safety Analysis Set)

Table 14.1.4.5 Concomitant Medications and Therapy (Intent-to-Treat Safety Analysis Set)

Table 14.2.1.1 Summary of Angioedema Attacks during Treatment Period (Full Analysis Set)

Table 14.2.1.2.1 Sensitivity Analysis Completed Schedules - Summary of Angioedema Attacks during Treatment Period (Full Analysis Set)

Table 14.2.1.2.2 Sensitivity Analysis Treatment Compliance - Summary of Angioedema Attacks during Treatment Period (Full Analysis Set)

Table 14.2.1.3 Analysis of Clinical Responder Rate – Achieving at least 50%, 70% or 90% Reduction Relative to Historical Data in NNA (Full Analysis Set)

Table 14.2.2.1.1 Summary of Breakthrough Angioedema Attacks Treated By CINRYZE (Full Analysis Set)

Table 14.2.2.1.2 Summary of Breakthrough Angioedema Attacks Treated By Non-CINRYZE C1-INH (Full Analysis Set)

Table 14.2.2.1.3 Summary of Other Breakthrough Angioedema Attacks Not Treated with C1-INH (Full Analysis Set)

Table 14.2.2.1.4 Summary and Change from Baseline on AE-QoL (Full Analysis Set)

Table 14.2.3.1 C1-INH Antigen, Functional C1-INH activity, Complement C4 and C1q (Intent-to-Treat Safety Analysis Set)

Table 14.2.3.2 Antibody Results (Intent-to-Treat Safety Analysis Set)

Table 14.3.1.1 Overall Treatment-emergent Adverse Events (TEAEs) (Intent-to-Treat Safety Analysis Set)

Table 14.3.1.2.1 Treatment-emergent Adverse Events by System Organ Class and Preferred Term (Intent-to-Treat Safety Analysis Set)

Document: \\SW20RND01\\VistaTempDir\Temp28232\\Shire\_0624\_209\_SAP\_v1 0.docx

Version Date: 21Jul2017

Version Number:

1.0

Template No: CS TP BS016 Revision 4 Reference: CS WI BS005

Effective Date: 01Apr2016

Author:

Table 14.3.1.2.2 Serious Treatment-emergent Adverse Events by System Organ Class and Preferred Term (Intent-to-Treat Safety Analysis Set)

Table 14.3.1.3.1 Treatment-emergent Adverse Events by Preferred Term (Intent-to-Treat Safety Analysis Set)

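### SAP 5.8.7 counts medications as concomitant through the 1-Month visit, but the Appendix III algorithm stops at an undefined end of treatment and puts later starts in a class with no planned table

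*SAP*

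**What the plan says.** **Concomitant, in the SAP text.** SAP 5.8.7: "Concomitant medications are any medications taken from the start of Dosing Visit 1 through the 1-Month Post-treatment Follow-up Visit". Protocol 6.5.2 sets the same period for data capture: "Concomitant medications taken from the start of dosing (Dosing Visit 1) through the 1-Month Post-treatment Follow-up Visit will be recorded in the CRF".

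**Concomitant, in the algorithm.** SAP Appendix III (9.3) classifies each record by its start and stop dates. With a known start and a missing stop, the rule for late starts is "If start date > end of treatment, assign as post treatment". With both dates known it is "If stop date >= study med start date and start date > end of treatment, assign as post study". A record with no start date at all is assigned to prior or concomitant, never to the post-treatment class. The SAP does not define end of treatment.

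**Prior.** SAP 5.8.7: "Prior medications are any medications received for the management of HAE within 12 months before Day 1", plus any other drug taken in the week before Dosing Visit 1. Under the algorithm a drug is prior only if its stop date falls before the first dose, and a drug with a start date but no stop date can never be prior.

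**Outputs.** SAP 9.1.1 plans Table 14.1.4.4 (prior) and Table 14.1.4.5 (concomitant). SAP 9.1.3 plans one medication listing, 16.2.4.4.1, whose title names prior and concomitant medications. No table or listing is titled for post-treatment or post-study medications.

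**The concern.** The SAP defines one derived variable in two ways, and a programmer cannot satisfy both. If the algorithm is followed, Table 14.1.4.5 will not contain what 5.8.7 says it contains.

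The follow-up month has safety content. SAEs are collected to 30 days after the last dose and other AEs to 7 days, so a drug started to treat a late event falls in the part of the window that the algorithm excludes. Capture through the 1-Month visit was also a deliberate extension in protocol Amendment 5. The study plans for a minimum of 6 completers. If the table had 6 subjects, one omitted subject would change the percentage for a drug class by 1/6, about 17 percentage points.

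The two definitions of prior differ as well. An HAE drug started before Day 1 and still being taken is prior under 5.8.7 but only concomitant under the algorithm.

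**Working it through.** The plan states no figure on this point to reproduce. The check follows one record through the algorithm and then measures the excluded period.

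**1. A drug started 10 days after the last dose.** SAP 5.8.7 makes it concomitant in every case. Taking end of treatment as the last dose, Appendix III gives:

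| Start date | Stop date | Appendix III class | In Table 14.1.4.5? |
|---|---|---|---|
| Known | Known | Post study | No |
| Known | Partial | Post treatment | No |
| Known | Missing | Post treatment | No |
| Partial | Any | Depends on imputed start | Sometimes |
| Missing | Any | Concomitant | Yes |

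A partial start is imputed to the earliest possible date, so the result depends on the calendar. In two illustrative cases with the day missing:

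- Last dose 22 December, drug started 1 January: imputed start 1 January, after the last dose, so post treatment.
- Last dose 6 January, drug started 16 January: imputed start 1 January, before the last dose, so concomitant.

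All three known-start rows therefore contradict 5.8.7, as do partial starts whose earliest date is after the cut-off. A drug started on treatment and continued into follow-up stays concomitant under both rules.

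**2. Length of the excluded period.** Inputs: 24 doses, 3 or 4 days apart (protocol Schedule 2), and a 1-Month visit 30 ± 2 days after the last dose (protocol Section 3).

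- Days from first to last dose = 23 × gap + 1. For gaps of 3, 3.5 and 4 days: 70, 81.5 and 93.
- Share of the 5.8.7 window after the last dose = follow-up days / (treatment days + follow-up days).
- Central case: 30 / (81.5 + 30) = 30 / 111.5 = 27%.
- Lowest: 28 / (93 + 28) = 28 / 121 = 23%.
- Highest: 32 / (70 + 32) = 32 / 102 = 31%.

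**3. An HAE drug ongoing at Day 1.** Its stop date is on or after the first dose, or missing, and its start is before end of treatment. The algorithm assigns it to concomitant. It is therefore in Table 14.1.4.5 and not in Table 14.1.4.4. SAP 5.8.7 divides the medication summaries by indication, so continuing prophylaxis appears under HAE long-term prevention.

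**The case against.** **Appendix III is headed as a partial-date convention, so it might not govern complete dates.** This fails: its first row handles a known start with a known stop.

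**End of treatment could mean the 1-Month visit.** The conflict would then vanish. But the documents call that visit post-treatment, and nothing in the SAP supports the other meaning. If it was intended, it needs to be written down.

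**Protocol 6.5.2 is a recording rule, and protocol Schedule 3 has a row for concomitant and post-treatment medications together.** This stands. A post-treatment class is not foreign to the protocol, and the contradiction is SAP against SAP rather than a departure from a protocol analysis.

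**The data are not lost.** This largely stands. Listing 16.2.4.4.1 may carry these records. Its title does not promise it, but nothing excludes them, and in a study this small a listing can be read line by line. It is still not the summary that 5.8.7 describes.

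A reader might infer three stronger things that the documents do not support:

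- *That background HAE prophylaxis goes missing, undermining the before-after attack comparison.* It does not: it is tabulated in 14.1.4.5. What is lost is its second appearance, in the prior table.
- *That efficacy results change.* SAP 5.7.1 has its own rule for rescue medication, based on timing and the recorded indication, and SAP 5.7.2 limits breakthrough attacks to the interval between first and last dose.
- *That 27% of medications, or all drugs started in follow-up, are omitted.* The 27% measures days, and records with missing starts and some with partial starts remain concomitant.

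The scope for attack treatments in follow-up is also limited. The attack diary runs only to the 1-Week visit, and supplemental CINRYZE is study drug with its own administration listing.

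**Conclusion.** The inconsistency is real and the SAP is wrong as written. For any drug with a known start date between end of treatment and the 1-Month visit, and for partial starts whose earliest date falls there, 5.8.7 and Appendix III give different classes, and the Appendix III class has no planned table. The two labels for that class also disagree with each other.

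The consequence is confined to descriptive medication summaries. The affected period is about 27% of the 5.8.7 window (23% to 31%), assuming end of treatment means the last dose. The number of medications involved cannot be derived from the documents.

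The mismatch on prior medications is secondary. It concerns which table shows an ongoing HAE drug, not whether it is shown.

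**What to change.** 1. In Appendix III, replace end of treatment with the date of the 1-Month Post-treatment Follow-up Visit in every row that assigns concomitant status, and state which date applies when that visit did not take place. Follow-up starts then count in Table 14.1.4.5, as 5.8.7 requires.
2. If the sponsor wants to separate follow-up starts, show drugs started after the last dose under a subheading of Table 14.1.4.5. Defining end of treatment and adding a post-treatment table would also close the gap.
3. Use one label for the post-treatment class in all rows.
4. Reconcile the two definitions of prior. One option that follows the 5.8.7 wording is to flag HAE drugs started before Day 1 and still ongoing so that they appear in both tables. A single-table convention would also work if 5.8.7 were reworded to match.

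Cost: wording in one appendix table and one derived variable, with no new data. The downside of item 4's first option is that ongoing drugs appear in two tables, so a footnote should warn against adding the counts.
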